STATISTICAL ANALYSIS PLAN

Evaluating a Digital Peer Mentoring Platform With College Student Populations

NCT05764785

August 2, 2023

This study was designed to examine whether using MentorPRO with a peer mentor – compared to peer mentoring-as-usual (control) - during a summer bridge program was related to significantly greater reduction in mental health symptoms and improvement in wellbeing indices. Inclusion criteria included elevated mental health symptoms, 18-years-old or older, English proficiency, and participating in the summer bridge program at University of Massachusetts Boston.

Data Analysis Plan from IRB Protocol:

- **Data analysis:** The data will be analyzed both quantitatively and qualitatively. The procedures are outlined below to address each of the research questions:
 - Research Question 1: What is the acceptability and feasibility of the MentorPRO mentoring program?
 - Recruitment, retention, and adherence to the MentorPRO mentoring program and application will be evaluated to determine the acceptability and feasibility of the program.
 - Acceptability of MentorPRO will also be assessed through open-ended questions and surveys commonly used to evaluate online programs.
 - Qualitative analyses will be conducted to evaluate the level of participants' engagement with mentors via the in-app chat messaging feature.
 - Mentors' responses to survey questions will examine initial mentor feasibility and acceptability of MentorPRO.
 - Research Question 2: Does mentoring with MentorPRO demonstrate an impact on efficacy for student academic outcomes (i.e., GPA) and indices of wellbeing (i.e., mental health, connectedness, academic self-efficacy, and overall well-being) among a diverse sample of incoming or first year college students?
 - Quantitative analyses will be conducted to determine whether level of engagement with mentors and the app (e.g., via frequency of in-app chat messaging, frequency of in-app survey completion and check-ins) relates to changes in academic outcomes and indices of wellbeing, as well as to broadly model how these domains change over the course of students' participation.
 - Group comparisons will be conducted to examine if there are differences in final mental health and wellbeing measures across groups (intervention and control). Baseline demographics and wellbeing indices will be used as covariates in analyses.
 - Exploratory analyses will also be conducted on the data to examine whether other trends or patterns emerge from the data.
- **Data integrity:**
 - In order to ensure quality control of the data collected via the Qualtrics survey, participants will be prevented from submitting multiple responses by enabling this feature within Qualtrics. Data will be checked for missingness.

The final Clinical Trials report findings will follow this analytic plan. We will report descriptive statistics for the sample and primary and secondary outcome measures. Power analysis will be performed to determine that the sample size is adequate to detect a statistically significant difference given the anticipated effect size. Using intention-to-treat analyses, we will conduct repeated measures ANOVAs with two time points (pre and post summer bridge program), to examine whether significant interactions emerge between time and assigned condition (MentorPRO vs. control) on main outcome measures (depression [PHQ-9] and anxiety [GAD-7])

self-reported symptoms and overall wellbeing) and secondary outcome measures (academic self-efficacy, sense of belonging to the university, and cognitive load). To correct for multiple comparisons, we will use a Bonferroni correction, $\alpha = .05$ divided by six tests, resulting in a final α of .008.

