- **Background literature with references:** A growing number of researchers have suggested more effectively leveraging more experienced peers to support first year students (Wilson & Gore, 2013). Assigning peer mentors through formal programs can help to address the fact that more marginalized students often struggle to recruit college-based mentors on their own (Gowdy et al., 2020; Hagler et al., 2021). Unfortunately, most peer mentoring programs emphasize nonspecific, relational approaches, and provide uneven training and oversight (Burton et al., 2022; Christensen et al., 2020), resulting in small to non-existent effects on students' psychological, academic, and behavioral difficulties (Christensen et al., 2020; DuBois et al., 2011; Raposa et al., 2019). A meta-analysis of 48 youth mentoring studies showed that the overall effect size of programs that target specific goals are double that of non-specific relational approaches overall, and three times more effective in improving academic, psychological, and social functioning (Christensen et al., 2020). Moreover, research on cross-age peer-mentoring programs emphasize the importance of peer training; peer mentors have moderate effects on mentees' outcomes overall ($g=0.45$), but there are no measurable effects ($g=0.03$) when there is low oversight (Burton et al., 2022). Particularly given the enormous potential of peer mentors to bridge growing gaps in student support, these studies suggest a need for college peer-mentoring approaches that (a) provide sufficient training and support of mentors (b) track and support students' early challenges; (c) are grounded in targeted, goal-focused, evidence-based approaches; and (c) are integrated with campus reporting systems. Moreover, mobile platforms can help to support and scale these approaches. Based on these principles, MentorPRO was developed in partnership with researchers, university staff, and students. Early evaluations of MentorPRO demonstrated that MentorPRO was both acceptable ([name] et al., 2023) and feasible ([name] et al., 2023). Propensity score matching with students at the same mentoring initiative indicated that

Investigator Protocol

greater engagement with peer mentors and greater engagement with a student support smartphone app, MentorPRO, are significantly related to better student academic outcomes and perceived wellbeing ([name] et al., in progress).

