- o Because students in the **MentorPRO** condition are being asked to do additional tasks (compared to students who are not in the MentorPRO condition), students in the MentorPRO condition will be allowed to participate in a raffle for a MacBook Air (valued at \$899) for the use of MentorPRO. Students in the MentorPRO condition are being asked to use MentorPRO and the Healthy Minds every day, resulting in up to 35 minutes of effort a day. Given this effort, we feel that this opportunity is adequate compensation. If all participants earn a similar number of chances, the probability of winning the MacBook Air is 1/25 (4 % chance).
 - 5 entries for messaging with their Peer Navigator each week through Aug 11
 - Now through July 28
 - July 28-Aug 4
 - Aug 5 - Aug 11
 - 1 entry for each Check-In before Aug 11
 - 5 entries downloading/installing/following directions to get onto Healthy Minds
 - 1 entry for every day of Healthy Minds use after initial use

Students in the MentorPRO condition *who have already consented to the study* will be informed of the raffle via text, email, and/or phone call and will be given the raffle information, including the attached PDFs (explaining the raffle, and how to get started with Healthy Minds). Questions will be answered by research staff.

Data Analysis

- **Data analysis:** The data will be analyzed both quantitatively and qualitatively. The procedures are outlined below to address each of the research questions:
 - o Research Question 1: What is the acceptability and feasibility of the MentorPRO mentoring program?
 - Recruitment, retention, and adherence to the MentorPRO mentoring program and application will be evaluated to determine the acceptability and feasibility of the program.
 - Acceptability of MentorPRO will also be assessed through open-ended questions and surveys commonly used to evaluate online programs.
 - Qualitative analyses will be conducted to evaluate the level of participants' engagement with mentors via the in-app chat messaging feature.
 - Mentors' responses to survey questions will examine initial mentor feasibility and acceptability of MentorPRO.
 - o Research Question 2: Does mentoring with MentorPRO demonstrate an impact on efficacy for student academic outcomes (i.e., GPA) and indices of wellbeing (i.e., mental health, connectedness, academic self-efficacy,

Investigator Protocol

and overall wellbeing) among a diverse sample of incoming or first year college students?

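### The SAP plans a power analysis to confirm sample adequacy, apparently after recruitment and with no effect size, target power or N fixed; it should report achieved N, intervals and the detectable difference instead

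*SAP*

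**What the plan says.** The last paragraph of the SAP commits to a future calculation: "Power analysis will be performed to determine that the sample size is adequate to detect a statistically significant difference given the anticipated effect size". The analysis is "repeated measures ANOVAs with two time points (pre and post summer bridge program"), testing the time-by-condition interaction on six outcomes. The significance level is .05 "divided by six tests, resulting in a final α of .008". No value or source is given for the anticipated effect, and no target power, standard deviation, pre-post correlation, dropout rate or N appears.

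The protocol has no sample-size calculation either. Number of Participants gives a programme capacity of up to 300 and expects fewer to join the research. Recruitment Methods has staff handing out postcards during the programming, which Study Duration dates June 12 to July 21. Under Payment/incentives, the raffle is open only to MentorPRO-condition students, is announced to those "who have already consented to the study", and carries these odds if entrants earn similar numbers of chances: "the probability of winning the MacBook Air is 1/25 (4 % chance".

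The protocol's only effect sizes are in its background literature: g = 0.45 for cross-age peer mentoring overall and g = 0.03 under low oversight.

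**The concern.** A power analysis helps with planning when the effect of interest and the target power are set before N is known. Here the order appears reversed, and the key input, "given the anticipated effect size", is left open. The sentence is worded to establish that the sample is adequate. It does not ask whether it is, and nothing follows if it is not.

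At stake is how a result with p above .008 is read. The paragraph asks whether significant interactions emerge and plans no confidence intervals. A report that first declares the sample adequate and then finds no significant interaction could be taken as evidence that MentorPRO adds nothing to ordinary peer mentoring, even if the data were compatible with a worthwhile benefit.

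**Working it through.** **Stated figures.** There is no N or power figure to reproduce. The alpha checks: .05/6 = .00833, given as .008. The raffle odds check: 1/25 = 4%.

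**Timing.** From July 21 (end of programming) to August 2 (SAP date) is 12 days. From June 12 to August 2 is 51 days, or 51/7 = 7.3 weeks of a 9-week trial. The first raffle entry period ends July 28, and its text already refers to consented students.

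**Inputs for the illustration**
- Alpha .008 (SAP), two-sided (assumed, as for an ANOVA F test).
- MentorPRO arm n1 = 25 (inferred from the raffle odds).
- Control arm n2 is not stated. I use 25, and 275 as the most the cap allows (300 − 25).
- Effect d = 0.45 baseline SD (protocol background, illustration only).
- Pre-post correlation r is not stated. I use 0.3 to 0.8, with equal variances at both times.
- No dropout and no clustering by mentor or cohort, which favours the trial.

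**Method.** With two time points, the time-by-condition test is a two-sample t test on change scores. In baseline SD units:
- SD of change = √(2(1 − r))
- SE = √(2(1 − r)) × √(1/n1 + 1/n2)
- noncentrality = d/SE, df = n1 + n2 − 2, power from the noncentral t

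Worked case, r = 0.5 and 25 per arm: SD of change = 1, SE = √(2/25) = 0.283, noncentrality = 0.45/0.283 = 1.59. The critical t on 48 df is 2.77, and power is 13%.

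| r | Power, 25 v 25 | Detectable at 80% | Power, 25 v 275 | Detectable at 80% |
|---|---|---|---|---|
| 0.3 | 9% | 1.21 SD | 20% | 0.87 SD |
| 0.5 | 13% | 1.03 SD | 30% | 0.73 SD |
| 0.7 | 25% | 0.79 SD | 54% | 0.57 SD |
| 0.8 | 41% | 0.65 SD | 77% | 0.46 SD |

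**Equal arms, d = 0.45.** Reaching 80% power at r = 0.5 takes 123 per arm. At 150 per arm (the full cap of 300), power is 89% at r = 0.5 and 73% at r = 0.3.

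**Baseline-adjusted variant.** The protocol also mentions baseline covariates. Replacing the SD by √(1 − r²), power at 25 per arm is 15% to 46% over the same correlations. With 275 controls it is 34% to 82%, passing 80% only at the top of the correlation range.

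**Precision.** At 25 per arm and r = 0.5, the 99.2% interval half-width is 2.77 × 0.283 = 0.78 SD. The 95% half-width is 2.01 × 0.283 = 0.57 SD. An estimate of zero would therefore not exclude 0.45 SD at either level.

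**The case against.** The strongest reply is that the documents do not show the sample to be inadequate. A reader might infer that the SAP's own figures prove it, but the SAP supplies only alpha. The 25 comes from odds that assume similar numbers of chances and concern raffle entrants. The control-arm size appears nowhere. The 0.45 is a background value for peer mentoring overall, never adopted here, and this trial compares peer mentoring with MentorPRO against peer mentoring without it. All of this stands, so the power figures are illustrations. It does not rescue the planned step: an effect smaller than 0.45 would lower power further, and the missing inputs are themselves the defect.

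Three other strong readings also go too far:
- That recruitment had definitely closed. The dates point that way, but no closing date is stated, and the reference to consented students identifies who hears about the raffle, not that enrolment had ended.
- That the trial could detect only very large effects. With more controls or a higher correlation, the detectable effect falls to around 0.5 SD.
- That a null result will be misread, or the effect size picked to suit. Neither document says how a non-significant result will be interpreted; this is a risk the wording leaves open, not a stated intention.

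**Conclusion.** The concern holds in limited form. The SAP plans an adequacy check that apparently follows recruitment, has none of its inputs fixed, and cannot set the sample size. That conclusion needs no assumption about arm sizes.

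How imprecise the trial is remains conditional. If about 25 students are in the MentorPRO arm, power for 0.45 SD in the planned analysis stays below 80% at every correlation tried, even with the largest control arm the cap permits. If enrolment was near 300 in equal arms, the sample could be adequate for that effect at correlation 0.5 or higher. The documents do not settle which applies, so the achieved N must be reported.

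**What to change.** Delete the adequacy sentence from the SAP and replace it with the following:
- State the achieved N per arm. If the sponsor confirms it, also state that recruitment was complete before the SAP was written and that no a priori sample-size calculation was made.
- For each of the six outcomes, report the between-group difference in change with a 99.2% confidence interval, which matches alpha .008. A 95% interval may be added.
- Beside each, give the smallest difference detectable with 80% power at the achieved N and alpha .008, stating the correlation and SD used.
- Do not compute power from the observed effect.
- Interpret non-significant results from the interval, not as evidence of no effect. Do not use exclusion of 0.45 SD as a decision rule unless the sponsor justifies that value for this contrast.

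The cost is SAP wording and minor reporting work, with no extra enrolment or data. The trial's stated ability to detect an effect becomes less favourable.

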 - All interested participants will read and sign an informed consent, after having time to ask questions to program staff and the research team. Then, they will complete an eligibility screener, and if eligible will complete the rest of the baseline survey.
 - Interested participants will then be prompted to take the first survey after consenting to the study (T1). Students will complete the DSP course for 6 weeks, and will receive peer mentoring during that time. For 3 weeks after the course, students will be able to contact their peer mentor with questions. At the end of the 9-week trial, students will receive a final survey (T2). The eligibility screener, informed consent, and the surveys will be administered via a Qualtrics link. At the conclusion of their participation, all participants will receive a debriefing statement explaining the study and where to find additional resources if needed.
 - Students will be assigned to the intervention or control condition based on what DSP cohort they are part of (a.m. or p.m. classes - the a.m. cohort will be assigned to the intervention/MentorPRO condition, while the p.m. cohort receives mentoring as usual).
 - Mentors will be matched with students who are assigned to both conditions, and therefore all mentors will receive all training materials. In addition to the training in program policies and relationship building provided to program peer mentors, all mentors will undergo training designed by the research team. Mentors will complete a brief orientation to the MentorPROUMB technology, followed by a 30-min interactive online course on providing supportive accountability, through MentorPRO UMB Academy which includes “knowledge checks” to ensure mentors are engaged and understanding the material and tracks progress to ensure course completion. Finally, mentees will be given access to an online orientation to MentorPRO UMB, which walks them

Investigator Protocol

through instructions about how to download and use the app. All study participants (mentors and student mentees) will have access to tech support within 24 hours from Academic Web Pages for any questions or issues that arise.

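### The SAP promises intention-to-treat, but its two-time-point ANOVA drops students without T2 and no method for missing T2 is named

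*SAP*

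**What the plan says.** The SAP's final paragraph sets out the analysis for the trial report: "Using intention-to-treat analyses, we will conduct repeated measures ANOVAs with two time points (pre and post summer bridge program". The test is the time-by-condition interaction on three main and three secondary outcomes, each at .05/6, given as .008.

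On missing data, the SAP has one sentence, under Data integrity: "Data will be checked for missingness". The protocol's Data Analysis section has the same sentence. Neither document defines the intention-to-treat set, names an imputation or likelihood method, or plans a sensitivity analysis.

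The part of the SAP carried over from the IRB protocol describes another comparison: "Group comparisons will be conducted to examine if there are differences in final mental health and wellbeing measures across groups (intervention and control", followed by "Baseline demographics and wellbeing indices will be used as covariates in analyses". The final paragraph opens with "The final Clinical Trials report findings will follow this analytic plan" and then names no covariate for the ANOVAs.

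Condition follows class timetable (protocol, Procedures Involved): "the a.m. cohort will be assigned to the intervention/MentorPRO condition, while the p.m. cohort receives mentoring as usual". There is one follow-up survey: "At the end of the 9-week trial, students will receive a final survey (T2".

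**The concern.** An intention-to-treat analysis should account for every student in the defined set, including those who do not return T2. A two-time-point repeated measures ANOVA cannot do so, because a student with T1 only has no change score. The analysed set, and hence the estimate, would depend on who answers the last survey.

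Some missing T2 is foreseeable. There is a single final survey at 9 weeks, and the protocol (Risks to Participants) lets students skip items or stop at any point. If the students lost from one class differ at T1 from those who stay, the completer comparison of change is distorted even with no true effect.

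A smaller matter concerns covariates. The classes were not formed by randomisation, so they may differ at T1. The SAP mentions baseline adjustment, but does not say whether it applies to the ANOVA or with which variables.

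**Working it through.** **The plan's own figure.** 0.05 / 6 = 0.00833, which rounds to the stated .008. Six tests at .008 give a Bonferroni bound of 6 x .008 = .048. Six outcomes with one ANOVA each use all six tests. Testing the final-score comparison on the same outcomes as well would give 12 x .008 = .096. The error budget therefore fits the ANOVA alone.

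**Equivalence.** With two time points, the interaction estimate is (mean T2 - mean T1 in MentorPRO) minus (mean T2 - mean T1 in control). It needs both scores from each student.

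**Inputs not in the documents (assumed).** Pre-post correlation r 0.5-0.7; equal SDs at T1 and T2; T2 loss of 10-30% in one arm; log-odds of loss rising by 0.5-1.0 per SD of the score that drives it; no true effect. The MentorPRO arm is taken as about 25, inferred from the raffle odds of 1/25 (protocol, Payment/incentives), which is not a stated sample size. Loss of 10-30% is then 0.10 x 25 = 2.5 to 0.30 x 25 = 7.5, or about 3 to 8 students.

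**Shift among completers.** Let q be the loss rate, z the standardised score driving loss and p(z) the probability of loss. The completers' mean of z moves by d = E[z p(z)] / (1 - q) in absolute value. Numerical integration gives d = 0.049 (q = 10%, slope 0.5) to 0.253 (q = 30%, slope 1.0).

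**Loss depends on T1, one arm.** Completers' T1 mean shifts by d and their T2 mean by r x d.
- Completer change: bias (1 - r) x d, from 0.3 x 0.049 = 0.015 to 0.5 x 0.253 = 0.127 SD. Simulation gave 0.0147-0.1269.
- Likelihood model using everyone's T1: bias about 0 (simulated within 0.0006).

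**Loss depends on T1 equally in both arms.** The two shifts cancel (simulated within 0.0013).

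**Loss depends on T2 itself, one arm.** Completers' T2 mean shifts by d and their T1 mean by r x d.
- Completer change: again (1 - r) x d, about 0.015-0.13 SD.
- Likelihood model: approximately (1 - r^2) x d, from 0.51 x 0.049 = 0.025 to 0.75 x 0.253 = 0.190. Simulation gave 0.0255-0.1973, slightly more at the top because selection on T2 also flattens the T1-T2 slope among completers.
- The likelihood bias is about (1 - r^2) / (1 - r) = 1 + r = 1.5-1.7 times the completer bias.

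**What a shift analysis would show.** If missing T2 values in one arm are moved by 0.25-0.5 SD, the effect moves by loss x shift: 0.10 x 0.25 = 0.025 to 0.30 x 0.5 = 0.15 SD.

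**Covariates.** With equal SDs, the change and T1-adjusted estimates differ by (1 - r) x the T1 gap. For an assumed gap of 0.3 SD that is 0.3 x 0.3 = 0.09 to 0.5 x 0.3 = 0.15 SD. In general the factor is 1 - r x SD2/SD1; with r = 0.7 and SD2/SD1 = 1.4 it is 1 - 0.98 = 0.02, and the two nearly coincide. With no true T1 difference, both tests held their level in simulation (.0077-.0081 at nominal .008).

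**The case against.** **Intention-to-treat may only mean analysis by assigned class.** The SAP tests assigned condition, and app use will vary, so the label may mean that students count in their cohort whatever their engagement. On that reading the sentence does not contradict itself. This stands as a reading, but it still gives no rule for a missing T2.

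**Differential loss is not documented.** Both arms receive $50 for T2, and the MentorPRO-only raffle gives no entry for completing it. A reader might infer that the trial's result will be biased. The documents do not support that: loss may be small, unrelated to scores, or equal in the two classes.

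**The mixed model is not better in every case.** This stands. Its advantage is shown for T1-dependent loss in one arm. For T2-dependent loss in one arm it is more biased than the completer analysis, so a shift analysis is needed too.

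**The primary analysis can be identified.** A reader might infer that the SAP leaves open whether the change analysis or the final-score comparison is primary. The text points the other way: the final paragraph ties the ANOVA to six named outcomes and spends all six Bonferroni tests on it, while the final-score comparison is carried-over IRB text. What stands is the narrower doubt about covariates.

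**The change test is not invalid because of chance imbalance.** A reader might infer that it is. Its rejection rate rises (.0133-.0225) only when one selects trials with an observed T1 gap above 0.3 SD; over all trials with equal class populations it holds .008.

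**Conclusion.** The main point holds on the text alone. The named model omits students without T2, and a check for missingness is not a method for handling it. As written, the analysis is of completers.

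The size cannot be known from the documents. Under the stated assumptions, bias from one-arm, T1-dependent loss is about 0.015-0.13 SD, and a likelihood model removes it. Equal T1-dependent loss in both arms cancels. One-arm, T2-dependent loss biases every method: about 0.015-0.13 SD for completer change and 0.025-0.20 SD for the likelihood model.

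The covariate point is secondary, at medium confidence. The ANOVA is most naturally confirmatory, but its adjustment is unspecified. If the classes truly differ at T1, choosing between change and T1-adjusted models is a trade-off that the data cannot settle: the change score misleads if the gap regresses, the adjusted model if it is stable. This should be fixed, but it does not undermine the design.

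**What to change.** Amend the SAP's final paragraph before T2 scores are examined; if they already have been, say that the change was made afterwards.

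1. Define the analysis set as all consented, eligible students with T1, by assigned cohort. First reconcile eligibility: the SAP's opening paragraph requires raised mental health symptoms, while the protocol's screening list (Recruitment Methods) omits them and presents itself as complete.
2. Fit the same time-by-condition test as a likelihood-based mixed model of T1 and T2 with unstructured covariance. With complete data it gives the same interaction estimate as the ANOVA. Keep the six tests at .008.
3. Report T2 completion by arm, and one missing-not-at-random shift analysis for the three main outcomes.
4. Name the baseline-adjusted comparison of final scores as a sensitivity analysis, list its covariates, and show it beside the T1 difference between the classes.

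No new data are needed. The cost is some added analysis work, and a sensitivity result that may disagree with the main one and would have to be reported.
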